3.2.6 Tumour shrinkage

Tumour shrinkage will be assessed using RECIST 1.1 tumour response. The absolute change and percentage change from baseline in sum of tumour size at each assessment will be calculated. Tumour size is the sum of the longest diameters (SLD) of the TLs. The percentage change in SLD at each week for which data are available will be obtained for each subject taking the difference between the SLD at each week and the SLD at baseline divided by the SLD at baseline multiplied by 100 (i.e., $[\text{week } n - \text{baseline}] / \text{baseline} \times 100$). The change from baseline will be obtained for each subject taking the difference between the SLD at each week and the SLD at baseline (i.e., week n - baseline).

The best percentage change in SLD from baseline or the minimum increase from baseline in the absence of a reduction from baseline based on all post-baseline assessments prior to progression or start of subsequent anti-cancer therapy.

If best percentage change cannot be calculated due to missing data, a value of +20% will be imputed as the best percentage change from baseline in the following situations (otherwise best percentage change will be left as missing):

- If a subject has no post-baseline assessment and has died;
- If a subject has new lesions or progression of NTLs;
- If a subject has withdrawn due to PD and has no evaluable TL data before or at PD.

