For lymph nodes, if the size reduces to < 10 mm, these are considered non-pathological.

However a size will still be given and this size should still be used to determine the TL visit response as normal. In the special case where all lymph nodes are < 10 mm and all other TLs are 0 mm, although the sum may be > 0 mm, the calculation of TL response should be overwritten as a CR.

TL visit responses subsequent to CR

A CR response can only be followed by CR, PD or NE. If a CR has occurred, the following rules at the subsequent visits must be applied:

- Step 1: If all lesions meet the CR criteria (i.e., 0 mm or < 10 mm for lymph nodes), the response will be set to CR irrespective of whether the criteria for PD or TL is also met (i.e., if a lymph node LD increases by 20% but remains < 10 mm).
- Step 2: If some lesion measurements are missing but all other lesions meet the CR criteria (i.e., 0 mm or < 10 mm for lymph nodes), the response will be set to NE irrespective of whether when referencing the sum of TL diameters the criteria for PD is also met.
- Step 3: If not all lesions meet the CR criteria, and the sum of lesions meets the criteria for PD, the response will be set to PD.
- Step 4: If, after steps 1 through 3, a response cannot be determined, the response will be set to remain as CR.

TL too big to measure

If a TL becomes too big to measure, this should be indicated in the database and a size ('x') above which it cannot be accurately measured should be recorded. If using a value of x in the calculation of TL response would not give an overall visit response of PD, then this will be flagged and reviewed by the study team blinded to treatment assignment. It is expected that a visit response of PD will remain in the vast majority of cases.

TL too small to measure

If a TL becomes too small to measure a value of 5 mm will be entered into the database and used in TL calculations, unless the radiologist has indicated and entered a smaller value that can be measured reliably. If a TL response of PD results then this will be reviewed by the study team blinded to treatment assignment.

Irradiated lesions/lesion intervention

Previously irradiated lesions (i.e., lesion irradiated prior to entry into the study) should be recorded as NTLs and should not form part of the TL assessment.

Any TL (including lymph nodes), which has had intervention during the study (for example, irradiation/palliative surgery/embolisation), should be handled in the following way:

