- Step 1: the diameters of the TLs (including the lesions that have had intervention) will be summed and the calculation will be performed in the usual manner. If the visit response is PD this will remain as a valid response category.
- Step 2: If there was no evidence of progression after step 1, the lesion diameter (for those lesions with intervention) will be treated as missing and scaled up as described previously as long as there remain $\leq 1/3$ of the TLs with missing measurements. If the scaling results in a visit response of PD then the subject will be assigned a TL response of PD.
- Step 3: If after both steps PD has not been assigned, then a scaled sum of diameters will be calculated, treating the lesion with intervention as missing, and PR or SD then assigned as the visit response. Subjects with intervention are evaluable for CR as long as all non-intervened lesions are 0 (or < 10 mm for lymph nodes) and the lesions that have been subject to intervention also have a value of 0 recorded.

At subsequent visits the above steps will be repeated to determine the TL and overall visit response. When calculating the previous minimum, lesions with intervention should be treated as missing and scaled up (as per step 2 above).

Once a lesion has had intervention then it should be treated as having intervention for the remainder of the study noting that an intervention will most likely shrink the size of tumors.

Lesions that split in two

If a TL splits in two, then the LDs of the split lesions should be summed and reported as the LD for the lesion that split.

Lesions that merge

If two TLs merge, then the LD of the merged lesion should be recorded for one of the TL sizes and the other TL size should be recorded as 0mm.

Change in method of assessment of TLs

Computerized tomography (CT) scan and MRI are the only methods of assessment that can be used within this trial. If a change in method of assessment occurs between CT scan and MRI this will be considered acceptable and no adjustment within the programming is needed.

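### SAP section 3.2.6 computes tumour shrinkage from the plain target-lesion sum and does not carry over the section 3.1.1.1 adjustment for lesions treated locally during the study

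*SAP*

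**What the plan says.** **Visit response (SAP 3.1.1.1, irradiated lesions/lesion intervention).** The rule opens: "Any TL (including lymph nodes), which has had intervention during the study (for example, irradiation/palliative surgery/embolisation), should be handled in the following way". Three steps follow.

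- Step 1 uses the plain sum, and a resulting PD stands.
- Step 2 sets the treated lesion to missing and scales the sum, provided no more than 1/3 of the target lesions are missing. It tests for PD again.
- In Step 3, if there is still no PD, "a scaled sum of diameters will be calculated, treating the lesion with intervention as missing, and PR or SD then assigned" as the visit response. CR requires the treated lesion itself to be recorded as 0.

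The rule also covers the nadir ("When calculating the previous minimum, lesions with intervention should be treated as missing and scaled up") and is permanent: "Once a lesion has had intervention then it should be treated as having intervention for the remainder of the study". The SAP gives its reason: "noting that an intervention will most likely shrink the size of tumors". Step 2 refers back to an earlier description of the scaling, but the SAP contains none.

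**Shrinkage (SAP 3.2.6).** The section begins "Tumour shrinkage will be assessed using RECIST 1.1 tumour response" and then gives its own definition: "Tumour size is the sum of the longest diameters (SLD) of the TLs". Absolute and percentage change are week n minus baseline on that sum. Best percentage change is "based on all post-baseline assessments prior to progression or start of subsequent anti-cancer therapy". The only missing-data rule is the +20% imputation. Neither intervention nor a scaled sum is mentioned. Section 4.2.7.8 reports best and per-visit change by randomised group and adds no adjustment.

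**The concern.** The SAP recognises that local treatment of a target lesion makes the sum look better for a reason other than study drug. It corrects for this in visit response and in the nadir. The shrinkage endpoint, which comes from the same measurements, is defined without that correction. A programmer working from 3.2.6 alone would sum all the target lesions, treated ones included.

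Two things are at stake. Shrinkage due to radiotherapy, surgery or embolisation could be summarised as change under the randomised arm. The study report could also show a sizeable decrease next to stable disease for the same patient and scan. Such patients stay in the data: section 2.2 gives radiotherapy on study treatment as an example of a deviation, but says deviations do not remove a subject from any analysis set, except possibly the PK set.

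**Working it through.** The SAP states no figure to reproduce, so the check applies the two sections to the same hypothetical scans.

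**Inputs**
- Change formula, from 3.2.6: (visit sum - baseline sum) / baseline sum x 100.
- Scaling limit, from 3.1.1.1 Step 2: no more than 1/3 of target lesions missing.
- Scaling formula, *assumed*: scaled sum = sum of untreated lesions at the visit x baseline sum of all lesions / baseline sum of the untreated lesions.
- PR threshold, *assumed*: a decrease of at least 30% (the SAP defers to CSP Appendix C).
- Lesion sizes: hypothetical.

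**Main example.** Baseline 30/30/30 mm (sum 90). One lesion is irradiated to 5 mm and the others are unchanged.
- Section 3.2.6: (5 + 30 + 30 - 90) / 90 = -25/90 = **-27.8%**.
- Section 3.1.1.1: 60 x 90/60 = 90 mm, so **0%**. Step 1 gives no PD, and the visit response is SD.

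**Other cases within the 1/3 limit**

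| Baseline (mm) | Visit (mm), treated lesion last | Plain sum | Scaled sum | TL response on scaled sum |
|---|---|---|---|---|
| 30/30/30 | 30/30/15 | -15/90 = -16.7% | 60 x 90/60 = 90, 0% | SD |
| 30/30/30 | 30/30/0 | -30/90 = -33.3% | 60 x 90/60 = 90, 0% | SD |
| 20/20/40 | 20/20/0 | -40/80 = -50.0% | 40 x 80/40 = 80, 0% | SD |
| five of 20 | four of 20, one 0 | -20/100 = -20.0% | 80 x 100/80 = 100, 0% | SD |
| 30/30/30 | 33/33/0 | -24/90 = -26.7% | 66 x 90/60 = 99, +10.0% | SD |

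In the last row the untreated lesions are growing, and the sign of the change reverses. In the second and third rows the plain sum passes the assumed PR threshold while the scaled response is SD.

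**Case with no discrepancy.** If every lesion, treated or not, goes from 30 to 20 mm, the plain sum gives (60 - 90)/90 = -33.3%. The scaled sum is 40 x 90/60 = 60, also -33.3%.

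**Effect on an arm mean.** Assume a near-even split of the 29 patients, 14 or 15 per arm. One patient like the main example then moves the mean best change by 27.8/15 = 1.9 to 27.8/14 = 2.0 percentage points, provided that value is the patient's minimum.

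**Which outputs are exposed.** The cut-off at progression or subsequent anti-cancer therapy is stated only for best percentage change. Per-visit absolute and percentage change have no cut-off. Under section 4.1.3, visit summaries are shown only where at least 10 subjects in either group have data, which limits how many visits appear in tables.

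**The case against.** The best defence is that 3.2.6 is silent and does not deliberately choose the plain sum. Its opening sentence points to RECIST 1.1 response. The 3.1.1.1 rules on small, split and merged lesions are not repeated there either, yet nobody would suppose they lapse. That is a fair reading, but it does not settle the matter. Those rules determine what diameter is recorded for a lesion, so they reach any sum built from it. The intervention steps are written for visit response and the previous minimum, and 3.2.6 goes on to state its own sum and formula. The general reference does not clearly import the scaling.

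A second defence is that the cut-off at subsequent anti-cancer therapy already removes irradiated patients. The SAP does not say whether radiotherapy counts. Sections 4.2.5.1 and 4.2.5.2 separate the two, but both sit under a common heading. If radiotherapy does count, best percentage change is protected in the irradiation example, but per-visit change is not.

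The points on size stand. Shrinkage is exploratory, nothing is tested, medians are reported alongside means, and on-study radiotherapy is listed as a deviation, so it is not expected as routine.

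A reader might go further and infer three things that the SAP does not support:
- *That shrinkage is biased in every patient with a treated lesion.* It is not if the minimum came before the intervention, if progression came first, or if the treated lesion shrank in proportion to the rest.
- *That a patient with two lesions, one of them removed, shows -50% against 0%.* One of two is more than the 1/3 limit in Step 2, so the SAP gives no clear scaled comparator.
- *That the response endpoints are affected.* ORR, BOR and DCR rest on visit responses, which already carry the intervention rule.

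**Conclusion.** The point holds in a limited form. As written, 3.2.6 omits an adjustment that 3.1.1.1 makes for a reason the SAP itself states, and the two sections can give different answers on the same scan. In the worked examples the plain sum shows about 17 to 50 percentage points of decrease where the scaled sum shows none, or growth. These figures depend on hypothetical lesion sizes and on the assumed baseline-proportion scaling.

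The exposure is change at visits after the intervention, and best change only when the minimum falls between the intervention and the cut-off. The SAP does not give the number of patients with a treated target lesion, and it may be zero. In a descriptive, exploratory endpoint from a terminated 29-patient study, this is a low-severity point that still merits correction, because a single such patient is visible in arms this small.

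**What to change.** 1. In 3.1.1.1, state the scaling formula that Step 2 refers back to. One option is the sum of the untreated target lesions at the visit, multiplied by the baseline sum of all target lesions and divided by the baseline sum of those untreated lesions, applied when no more than 1/3 of target lesions are missing.
2. In 3.2.6, state that from the date of intervention the sum used for absolute, percentage and best change is this scaled sum, and that it is missing when scaling is not allowed.
3. Flag the affected patients in the tumour-size listing.

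This works whichever way radiotherapy is classified for the best-change cut-off. The cost is a few lines of text and slightly more programming, since the visit-response derivation already needs the scaled sum. There may be a few missing values, and the reported shrinkage may be slightly less favourable.

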The assessment of progression of $\geq 20\%$ increase in the sum diameters of TLs compared with the nadir is at the first progression time point relative to the nadir (the smallest sum of diameters and this may be at baseline or subsequent follow-up visit). The confirmed scan confirms the persistence of the $\geq 20\%$ increase relative to the nadir.

- And/or significant progression (worsening) of non target lesions (NTLs) or new lesions at the confirmatory PD time point compared with the first time point where progression of NTLs or new lesions identified.
- And/or additional new unequivocal lesions at the confirmatory PD time point compared with the first time point new lesions identified.

Patients who discontinue treatment for reasons other than progression would undergo a 3-month follow-up. Progressions occurring during this follow-up will not necessarily have a second confirmatory scan.

Following approval of CSP version 2.0, objective tumour assessments every 8 or 12 weeks will only be carried out for Group B patients up to disease progression or up to 3 months following treatment discontinuation, and confirmation of progression will only be required for Group B patients who continue to receive MEDI4736 following progression, while patients discontinuing treatment may not have scans to confirm progression. Following approval of CSP version 2.0, patients in Group A will not have tumour assessment scans.

RECIST 1.1 without confirmation of progression will be regarded as primary in terms of the efficacy reporting. A sensitivity summary requiring confirmation will be conducted. The confirmation should occur at least 28 days from the first scan documenting radiological progression.

At each visit for the site investigator data, an overall visit response will be programmatically determined - using the information from TLs, NTLs and new lesions.

RECIST outcomes (i.e., PFS and ORR etc) will be calculated using a computer program for site investigator data.

RECIST results based on blinded independent central review were planned in the original protocol, but were not included in version 2.0 of the protocol, and no such review was performed.

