4.1.4 Handling missing data

In general, other than for partial dates, missing data will not be imputed and will be treated as missing.

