4.2.7.8 Tumour shrinkage

The best absolute change in target lesion tumour size from baseline, and percentage change in target lesion tumour size from baseline will be summarised using descriptive statistics and presented at each time point by randomized treatment group.

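### SAP section 3.2.6 contradicts itself on whether the scan at progression counts towards best percentage change in tumour size

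*SAP*

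**What the plan says.** Section 3.2.6 of the SAP takes the best percentage change in the sum of longest diameters, or the smallest increase if there was no reduction, "based on all post-baseline assessments prior to progression or start of subsequent anti-cancer therapy".

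If that quantity cannot be calculated because data are missing, +20% is substituted in three situations only; in every other case the value stays missing. The three situations are:

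- Death without follow-up imaging: "If a subject has no post-baseline assessment and has died"
- Progression outside the target lesions: "If a subject has new lesions or progression of NTLs"
- Withdrawal for progression without usable measurements: "If a subject has withdrawn due to PD and has no evaluable TL data before or at PD"

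Section 4.1.4 offers no other imputation: "In general, other than for partial dates, missing data will not be imputed and will be treated as missing".

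Section 3.2.6 also calculates the change from baseline at every assessment, without limiting this to scans before progression. Section 4.2.7.8 reports both kinds of result: "The best absolute change in target lesion tumour size from baseline", and percentage change presented by time point.

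**The concern.** The main rule and the third imputation condition answer the same question differently. The main rule stops before progression. The third condition asks whether evaluable target-lesion data exist before or at progression, and that matters only if a measurement at progression can be used. Two programmers could work from this one section and derive different datasets.

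The literal version also orders patients oddly. Someone withdrawn for progression with nothing measured enters the summary at +20%. Someone whose target lesions were measured and had grown by 20% or more drops out. That exclusion depends on the outcome, and it falls within efficacy summaries that sections 2.1.1 and 4.2.7 base on all randomised patients.

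**Working it through.** The SAP states no figure for this rule, so there is none to reproduce. The check has three steps.

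**1. Which patient falls through.** Take a patient whose first evaluable post-baseline scan shows progression by target lesions alone, and who is then withdrawn for progression.

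- No scan precedes progression, so the main rule has nothing to work on.
- First situation: not met, because a post-baseline assessment exists. A later death does not change this.
- Second situation: not met, because there is no new lesion and no non-target progression.
- Third situation: not met, because evaluable target-lesion data exist at progression.
- Section 4.1.4 adds nothing, so the value stays missing.

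**2. What kind of value is lost.** Section 3.1 defines the nadir as "the smallest sum of diameters and this may be at baseline or subsequent follow-up visit". At the first evaluable post-baseline scan the only earlier measurement is baseline, so baseline is the nadir. Target-lesion progression there means growth of at least 20% from baseline, with an absolute increase of at least 5 mm. Every value lost by this route is therefore +20% or worse.

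The two readings give the following for test patients (the percentages are illustrative):

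| Patient | Progression scan excluded | Progression scan included |
|---|---|---|
| Target lesions +35% at first scan, no other progression, withdrawn | missing | +35% |
| Withdrawn for progression, no evaluable target-lesion data before or at it | +20% (imputed) | +20% (imputed) |
| Target lesions -30% at first scan, but a new lesion | +20% if the excluded scan counts as missing data, otherwise missing | -30% |

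**3. How far an arm mean could move.** Let *n* be the patients in the arm, *k* the number lost in this way, *x* their value and *m* the mean of the others. The mean is *m* when they are left out and [(n - k)m + kx]/n when they are included. The shift is k(x - m)/n.

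Section 1.3 gives 29 randomised patients and a planned 1:1 ratio, so 29/2 = 14.5, or about 14 to 15 per arm. I use n = 15. The SAP gives no *m*, *x* or *k*. The assumed ranges are m from -40% to -20%, x from +20% to +50%, and k of 1 or 2.

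- k = 1, smallest shift: (20 + 20)/15 = 2.7 points
- k = 1, largest shift: (50 + 40)/15 = 6.0 points
- k = 2, smallest shift: 2 × 40/15 = 5.3 points
- k = 2, largest shift: 2 × 90/15 = 12.0 points
- k = 0: no shift

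**The case against.** The strongest reply is that the SAP means to include the progression scan and only words it loosely. Section 3.2.5 defines best overall response with similar language about assessments before RECIST progression, yet it keeps a category for progressive disease and goes on to use all data up until the first progression. If the phrase truly excluded the progression scan, a patient progressing at the first scan could not be classed as progressive disease. The third condition in section 3.2.6 points the same way. This stands as evidence of intent. It does not settle the text, because section 3.2.6 has no clarification like the one in section 3.2.5.

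Three stronger readings are tempting, and the SAP does not support them.

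- **That the shrinkage summary is biased favourably.** This follows only if the literal rule is programmed and such patients exist. Nor does the direction hold for every patient: the last row of the table shows that excluding the scan can also discard real shrinkage when progression is by a new lesion.
- **That measured growth of +35% with a new lesion is replaced by +20%.** Imputation applies only when the value cannot be calculated because data are missing. A measured value set aside by rule is not clearly missing data, so the text does not plainly order this.
- **That these patients' growth is hidden.** The by-visit changes retain the progression scan, and the progression counts as an event for progression-free survival under section 3.2.1.

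It is also fair to say that little depends on this result. Efficacy is exploratory (section 1.1), section 1.3 judges 29 patients too few for comparing the groups, and section 4 rules out hypothesis testing.

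**Conclusion.** The internal conflict in section 3.2.6 is real and should be resolved. Under the literal reading, measured target-lesion-only progression at the first evaluable scan goes missing, while unmeasured progression counts as +20%. The error from that loss runs towards more apparent shrinkage, provided the remaining patients average below the lost values.

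The conclusion is limited to the best-change summary. The number of affected patients is unknown and may be zero. The shifts of 2.7 to 6.0 points for one patient and 5.3 to 12.0 for two rest wholly on the assumed inputs above. They show that one or two patients matter in arms this small; they do not estimate a bias in this trial. No hypothesis test or primary safety conclusion is affected.

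**What to change.** Reword section 3.2.6 so that best percentage change uses all post-baseline assessments up to and including the one at which progression is first documented, and before any subsequent anti-cancer therapy. State that +20% is imputed, in the listed situations, only when no evaluable target-lesion measurement exists at or before progression. Both changes agree with the existing third condition. Say also that the best absolute change in section 4.2.7.8 uses the same set of scans.

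The cost is a sentence or two of SAP text and a small programming change, with no new data. The best-change summary may look slightly less favourable if affected patients exist.
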